4.3 Phase 1: Design and Development of the Virtual Reality Experience

Objective 1: Work with an interdisciplinary team to collaboratively develop a prototype that simulates the MRI environment and experience at BCCH in VR.

The media will be co-developed with a multidisciplinary team of stakeholders, including patient and family partners. Considerations for designing the resource have been informed by Gitlin (2013).²² In principle, the developed media will integrate an animated character that will guide the user through a series of tasks. The user will be encouraged to pivot, rotate, and semi-independently explore the virtual environment. The virtual environment will be created using any combination of 360 video and UNITY, a cross-platform game engine used for 3D environments (**Table 3**).

Table 3. Considerations for designing the VR media, adapted from Gitlin (2013).²²

Domain	Program Elements
Target of Intervention	Individual Family and social network
Area Targeted	Reduce anxiety and non-compliant behaviours that necessitate sedation Increase knowledge about the MRI procedure and environment Improve skills required for successful MRI (e.g. holding breath)
Delivery Technique	Multiple iterations, tailored to children of different age groups (4-12 and 13-18 years) and their caregivers Needs assessment driven
State of intervening	Prevention of sedation
Delivery mode	Virtual Reality Booklet Mock MRI
Dose and intensity	Frequency of contact (TBD) Length of time engaging (TBD)
Immediate and potential delivery setting	Hospital, clinic, or medical office (immediate) Mobile technology (immediate) Home (potential) Community (potential)
Characteristics of interventionists	Self-Guided delivery
Potential funding streams to support the intervention if proven effective	Costs associated with training (TBD) Costs associated with technology (TBD) Cost benefit to healthcare systems (TBD)

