A minimum of 93 participants (31 participants per group) aged 4-to-13 will be recruited through convenience sampling, consented, and randomized by staff to one-of-three preparation programs (VR, mock MRI, or booklet). Details of the comparison groups are outlined in **Table 4**. Given the restricted availability of the simulator, child life specialists, and the availability of participants, we are unable to fully randomly allocate participants. As such, participants will be randomly assigned to the intervention options available according to their individual availability (using Research Randomizer <https://www.randomizer.org/>). For example, if a participant is available on a Thursday that virtual reality and booklet are available, they will be randomly allocated to one of these interventions.

This phase will have open recruitment to all children and adolescents interested in participating, such that participants may not be BCCH patients scheduled for an MRI. This recruitment strategy was selected due to the resource constraints associated with limiting the evaluation group to MRI patients only.

Table 4. Details of the comparison groups.

	VR Simulation	MRI Preparation Booklet	Mock MRI
Facilitator	Research Assistant	Research Assistant	Child Life Specialist
Location	BCCH	BCCH	Simulation Room
Content	Refer to The Virtual Reality Simulation	Refer to MRI Preparation Book	Individualized intervention in physical simulator.

The different interventions will be held in separate private rooms located in BCCH, such that the VR and booklet groups will not have prior exposure to the imaging centre or the simulation room in advance of their assessment. This is to simulate our intended delivery in hospital, medical office, or clinic settings but minimize alternative explanations associated with testing in the simulation room where assessments will take place (previously described in **Table 3**).

Data will be collected throughout the implementation process (**Figure 3**). The predictive variables (demographics and relevant history, and delivery type) will be captured at the start of the session. The primary outcome variable is likelihood of success (pass/fail) of the MRI simulation, and will be measured at the end of the assessment. Anxiety will also be measured at three time points. Usability testing will be conducted throughout to capture possible quality improvements and amendments to each of the program delivery modes.

Inclusion/Exclusion Criteria

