Participants must be between the ages of 4-to-13 years to be included in the evaluation.

The following exclusion criteria, which have been noted in previous studies conducted using virtual reality programs, will be adopted for this project:

- mental disability (content not appropriate)
- significant visual and auditory impairment (this program focuses on auditory and visual cues)
- inability to speak or understand English (content and study staff are English speaking)
- history of seizures or epilepsy (triggered by virtual reality)
- facial or head wounds (cannot wear the virtual reality headset)

Implementation Plan

[figure not shown]

Figure 3. Implementation process.

The testing phase of the implementation process, depicted in Figure 3 will be completed over two hours, and will involve the following steps:

- 1) Participants and parents/guardians are greeted by staff and enter the intervention room.
- 2) Staff will obtain written consent from parents and verbal assent from children (5 minutes).
- 3) Participants will complete the Venham Picture Test (VPT) with staff (pre-test). In parallel, parents will complete the Short STAI on the iPad. (5 minutes)
- 4) Staff will reveal the allocated delivery mode (VR, mock MRI, or booklet) to the participant and explain the procedure.
- 5) Staff will ask participants to indicate on the Smileyometer how good they think the intervention is going to be.^{30,31} This will give a measure of expectation that can indicate whether or not the participant is subsequently let down by the activity or pleasantly surprised.
- 6) Staff will measure the participant's interpupillary distance using sliding calipers.
- 7) Participants will be given 45 active minutes to engage with the intervention. Groups include:

Group 1 (VR): The VR group will receive a virtual reality simulation designed during Phase 1 of this study.

Group 2 (mock MRI): The mock MRI will be provided by the CLS, according to the current care plan which consists of exposing children to the mock MRI, medical devices, and procedures. The mock MRI is located within the BCCH medical imaging facility.

Group 3 (booklet): The standard MRI preparation booklet group will provide access to a series of printed photos and text showing the MRI experience step-by-step to help prepare for the MRI.

- 8) Participants will be asked to indicate on the Smileyometer how good they actually thought the activity was overall (1 minute).

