Measure	Immediate Outputs	Intended Outcome
Primary		
MoTrak®	# of participants "prepared" to be scheduled for an effective MRI	
Improve access to MRI preparation for children who:
 
 - Live out of town - Would like to practice skills at home - Have mobility issues 
Improve non-sedation rates for MRI scans.

Venham Pictoral Test & Short STAI	# of participants with reduced anxiety # of parents with reduced anxiety	
Improve access to MRI preparation materials.
 
Improve behavioral compliance during medical procedures.

Secondary		
Smileyometer	# of participants who find the delivery mode fun and engaging to use	
Improve acceptability of preparation materials.
 
Improve satisfaction.

USE Questionnaire	# of parents who find the preparation materials useful	
Improve acceptability of preparation materials.
 
Improve satisfaction.

Natural Choice Selection	# of participants who select the booklet # of participants who select the mock MRI # of participants who select virtual reality # of participants who select none	Identify preference for engaging. Identify frequency of contact and time engaging.
Length of Stay	Minutes spent per segment	Improve hospital efficiency
Guided Survey	# of participants who find the booklet fun, easy to use, and good for learning about the MRI experience # of participants who find the mock MRI fun, easy of use, and good for learning about the MRI experience # of participants who find the virtual reality game fun, easy of use, and good for learning about the MRI experience	Improve utility of MRI preparation materials. Identify frequency of contact and time engaging.
Interpupillary Distance	Average interpupillary distance per age	Improve headset configuration.

Primary Measures

Predictive Success in Avoiding Sedation

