For the purposes of this evaluation, we will define total LoS as the duration, in minutes, from starting the *preparation* segment to completion of the simulated *assessment*. Inter-segment times will also be recorded. Preparation time will be capped at 45 minutes. Assessment time will be capped at 20 minutes. Start of preparation will be noted as time when study staff finish describing the intervention and indicate it is time to begin the active preparation. Time will stop when the participant is “discharged” from the MRI simulation, before the natural choice selection exercise and debriefing process begins. Time spent transitioning between activities or breaks required for reasons unrelated to the evaluation will not be counted towards overall LoS.

Interpupillary Distance

Interpupillary Distance will assume normal conditions and be measured objectively before preparation using Pryor's (1969) method³⁶ to ensure appropriate set up of the virtual reality device.

[figure not shown]

FIG. 1. Formula for interpupillary distance.

Usability Testing

The Smileyometer – 1 minute

The Smileyometer^{30,31} is an instrument used for measuring the opinions of technology in children, and has been validated in multiple studies assessing educational materials and software. The Smileyometer is based on the Visual Analogue Scale,³⁷ consisting of a 5-point Likert scale that uses pictorial representations. Participants are asked to point to the face they relate to.

Guided Survey – 10 minutes

The RA will ask the participant several open-ended questions on the preparation materials according to three separate criteria of fun, ease of use, and how good it was for learning about the MRI experience.

USE Questionnaire – 10 minutes

The USE Questionnaire²³ will be administered to the parents/guardians after the mock MRI only. This will allow participants to compare the VR application to the “effective MRI” experience. The USE Questionnaire is a 7-point Likert rating scale that has been well-validated to assess a program’s usefulness, ease-of-use, ease of learning, and satisfaction.

Analysis and Interpretation

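### Interpupillary distance is reported only as a mean per age, which cannot show the spread of children that a headset must fit

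*Combined protocol and SAP*

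**What the plan says.** Section 4.4 has two tables numbered 4. The second, on outputs and outcomes, lists interpupillary distance as the last secondary measure. Its immediate output is "Average interpupillary distance per age" and its intended outcome is "Improve headset configuration".

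Step 6 of the Implementation Plan has staff measure each participant's "interpupillary distance using sliding calipers", with no restriction to the VR group. The Interpupillary Distance paragraph says that this is done before preparation, "to ensure appropriate set up of the virtual reality device".

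Analysis and Interpretation does not mention the measure. Its descriptive analysis is confined to demographics and relevant history.

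On numbers, "A minimum of 93 participants (31 participants per group) aged 4-to-13 will be recruited through convenience sampling". The plan does not define the width of an age class for this output. The only age bands appear in Table 3 of section 4.3, where the media are to be "tailored to children of different age groups (4-12 and 13-18 years"; those bands concern media design.

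**The concern.** The output does not match its purpose. A headset is set for individuals, so the useful quantities are the spread at each age and the settings that would cover most children. Two ages with the same mean can need quite different adjustment ranges, and a mean alone cannot separate them. As listed, the output would not tell the team which settings suit most children, or at which ages the device stops fitting.

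This bears on later use more than on the trial itself. Section 4.3 foresees self-guided delivery and, potentially, a low-cost viewer sent to families at home, where staff may not be present to measure the child.

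A lesser point is efficiency. If each age is summarised on its own, every mean rests on few children and takes nothing from neighbouring ages.

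**Working it through.** **What the plan reports.** The outputs table gives a mean per age. The measure's own paragraph gives a use in the session. The analysis section gives nothing. No measure of spread appears in any of the three. There is no planned figure to reproduce: the documents give no SD, precision target or sample size for this measure.

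**Inputs from the documents.** N = 93. Ages 4 to 13, which is 10 classes if age is taken in whole years. All participants are measured.

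**Assumptions (not in the documents).** Whole-year classes, ages evenly spread, constant within-age SD of 3 mm (range 2 to 4 mm).

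**Children per age.** 93/10 = 9.3, or about 8.4 if 10% drop out. Recruitment is by convenience sampling with no age quota. Even if each age were equally likely, the 5th to 95th percentile of the number at one age would be 5 to 14.

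**Single-age mean.** The 95% half-width is t(0.975, n−1) × SD/√n. With n = 9.3 and SD = 3 mm:

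- 2.29 × 3/√9.3 = 2.25 mm
- 1.5 mm at SD 2 and 3.0 mm at SD 4

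**Linear regression on age, all 93 children.** With ages evenly spread over 4 to 13, the mean age is 8.5 and the variance is 8.25. The 95% half-width at age a is 1.99 × SD/√93 × √(1 + (a − 8.5)²/8.25). With SD = 3 mm:

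- mid-range: 1.99 × 3/√93 = 0.62 mm
- ages 4 and 13: 0.62 × √(1 + 4.5²/8.25) = 0.62 × 1.86 = 1.15 mm

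**Ratio of half-widths.** 2.25/1.15 = 2.0 at the end ages and 2.25/0.62 = 3.6 at mid-range. The SD cancels, so the ratio depends only on the number per age, the even spread and the form of the trend. With a quadratic trend it falls to about 1.5 to 2.7. Part of the ratio comes from the larger t multiplier on few degrees of freedom. On standard errors alone it is 1.7 to 3.2 (linear) or about 1.3 to 2.3 (quadratic).

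**Spread that a mean omits.** If values at one age are roughly normal, the 5th to 95th percentiles lie 1.645 × SD either side of the mean. That is ±4.9 mm at SD 3 (±3.3 at SD 2, ±6.6 at SD 4).

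**Would an SD per age be enough?** With 9 children, the 95% confidence interval for an SD runs from 0.68 to 1.92 times its estimate. The spread is therefore better estimated by pooling across ages than age by age.

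**The case against.** The case for leaving the plan alone has several parts.

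- *The measure is minor and already used child by child.* This stands. Set-up in the session can draw on the child's own value, so no participant is fitted by an age mean. The measure does not enter the pass/fail outcome, the anxiety analysis or the sample size, nor is it named among the outcomes for the economic phase. This lowers the importance of the point. It does not make a mean informative about spread.
- *The table lists headline outputs, and an SD can be added later.* This is true, since the data will exist. But the analysis section adds nothing for this measure, so the table is all the plan commits to.
- *Age classes may be wider than one year.* This is possible, because the class is undefined. Wider classes hold more children and weaken the efficiency argument. They still show no spread, and they mix in whatever growth occurs within the class.
- *The regression comparison is a favourable case.* This is partly right. It assumes an even spread of ages and a smooth trend, and the gain is smaller with a quadratic.

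Two stronger readings are tempting. A reader might infer that single-age means are two to four times less precise than needed. The documents give no required precision, no SD and no headset tolerance. With 9 children the half-width is 0.77 SD, or 1.5 to 3.1 mm for SDs of 2 to 4 mm. Against assumed targets of 0.5 to 3 mm, the ratio runs from 1.5/3 = 0.5 to 3.1/0.5 = 6.1, so under some assumptions the means are precise enough. A reader might also infer that chance steps between adjacent ages will be reported as growth. The plan contains no such comparison.

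**Conclusion.** The point holds at low severity. The only planned output for interpupillary distance is a mean per age, and this cannot serve the stated aim of improving headset configuration because it does not describe spread. That conclusion needs no numerical assumption.

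The efficiency argument is secondary and conditional. Given whole-year ages, evenly spread, single-age intervals are about 2.0 to 3.6 times as wide as those from a linear age regression on the same 93 children, or about 1.5 to 2.7 times as wide as those from a quadratic. This compares two ways of using the same data. No shortfall against a target is claimed.

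**What to change.** Replace the table's output with a regression of interpupillary distance on age in all measured children, adding a quadratic term if the fit needs it. Report by age the fitted mean and the 5th-95th percentile prediction range, with the observed SD, minimum and maximum. State how age enters the model and, for any tabulated summaries, how wide the age classes are. If the team has the adjustment range of the chosen headset, which the documents do not give, also report the share of children outside it.

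The cost is a few lines of analysis, with no new data, visits or participants. The downside is the smooth-trend assumption, together with the constant and roughly normal scatter behind the prediction range. A plot of the residuals against age would check these.

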Any medical staff depicted in the virtual world will be dressed in common professional attire to improve realism. An animated character will guide the user in the tour. Filming will be dependent on access to resources, but will likely be carried out using GoPro Fusion (360-degree camera) in the medical imaging facility at BCCH. The video components will then be stitched together, and the VR tour will be available using a variety of low-cost VR systems, accessible through a public-facing website. Since filming will occur in the hospital, it may occur over multiple iterations to ensure that patients and/or medical records are not inadvertently filmed.

To promote the self-guided nature of our proposed delivery, the virtual interaction will begin with a tutorial explaining how to use the application. When ready, users will be invited to be virtually guided through the MRI procedure. They will be able to pause the experience at any time. The content may include experiences such as:

1. Entering the medical imaging facility
2. Preparing for the scan (e.g. changing into a gown, checking height/weight, removing metal)
3. Additional information will be provided about the procedure, including:
 - What MRI is and the sounds it will make
 - The importance of staying still
 - What intravenous contrast (GAD) is
 - What equipment to expect
 - i. Knee coils
 - ii. Head coil
 - iii. Hand coils
 - iv. Foot coils
 - v. Leg coils
 - vi. Body coils
 - vii. Shoulder coils
 - viii. Seatbelts
 - Other information, as identified
4. Receiving numbing cream, and an IV
5. Choosing if they want to be accompanied during the scan
6. The two MRI rooms
7. The opportunity to freely explore the room and medical devices, such as the MRI machine, the patient table, the murals on the walls, types of coils, and straps.

The character will also guide the user through the MRI sequence. Content may include:

1. Wearing ear protection and headsets
2. Watching a movie
3. Talking to the MRI Technologist out loud
4. Using the emergency call bell, if required
5. The control room where the Technologist goes
6. Laying on the table and being strapped into place using the coils and seatbelts
7. Entering into the bore of the MRI machine

8. The red light used to center the patient's body for the pictures
9. Starting and completing the scan (i.e. wait a pre-designated amount of time inside the bore, before easing the patient outside the scanner).
10. Receiving intravenous contrast liquid (if applicable)

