- 9) Participants will be informed that they will now be completing a simulation test with the MRI scanner. Participants will be reminded of their free and informed ongoing consent.
- 10) The participant will be transferred to the simulation room, located in the medical imaging center at BCCH. Upon entering the simulation room, participants will verbally complete the VPT with staff (during test). In parallel, parents will complete the Short STAI on the iPad. (5 minutes)
- 11) Participants will be guided through a mock MRI and be assessed using MoTrack®, an objective head motion tracking system.³² The simulation will be completed over 20 minutes and will involve progression through the “MRI procedure”, remaining in the bore for 8 minutes. All participants will receive the same type of simulated scan. We will not be simulating any invasive procedures that can sometimes occur during the MRI (i.e. an IV or intravenous contrast liquid). Please note that this assessment involves a mock procedure using the simulator, not a real MRI.
- 12) Immediately following the simulation, participants will verbally complete the VPT with staff (post-test). In parallel, parents will complete the Short STAI on the iPad. (10 minutes).

- 13) Users will be asked to indicate on the *Smileyometer* how they thought the preparation activity was overall in preparing them for the MRI. Parents/guardians will be asked to complete the USE Questionnaire.
- 14) Staff will ask the user open-ended questions on the preparation materials according to three separate criteria of fun, ease of use, and how good it was for learning about the MRI experience. The final usability assessment will take a total of 10 minutes.
- 15) After the session is "complete", children will be told that they "happen to have some time left" so they can play with any of the preparation materials offered (VR, Mock MRI, Booklet) for 5-minutes if they want to "because they did so well during the activity." This will give children a natural choice selection and will be used to gauge preferences for the activities.
- 16) A verbal session debrief will include an opportunity for questions to mitigate any residual feelings of discomfort or anxiety that may arise from the project's activities.

Outcome Measures

The measures used to evaluate the intended outputs and outcomes associated with this project are outlined below (**Table 4**).

Table 4. Outputs and outcomes associated with the project.

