The predictive success in avoiding sedation will be measured using Motrak® software assessment. MoTrak® uses a sensor attached to the participant's head to determine the position of the head in space relative to a transmitter located within the simulator. The sensor records angular rotations as well as positional displacements from an initially calibrated position. This information is displayed and logged by the program in real-time, allowing objective observation of head motion in an MRI simulator.³² The fail threshold is set at 3mm of movement in any of the positional displacements (x,y,z), which is in accordance with imaging protocols at the Hospital.

Child Anxiety: Venham Picture Test – 5 minutes

Anxiety assessment with children will be completed in pictorial form to better adapt to the cognitive and communicative abilities and styles of younger children. The Venham Picture Test has been well-validated in children for assessing procedural anxiety^{33,34}, and comprises eight cards which two figures on each card, one anxious character and one non-anxious character. The children will be asked to point at the figure they feel most like at that moment. All cards will be shown in their number order. If the child points at the anxious figure, a score of one is recorded and if the child points at the non-anxious character, they will be given a score of zero. Children will complete the at three timepoints (before, during, after the mock MRI).

Secondary Measures

Parental Anxiety: Short State-Trait Anxiety Inventory (Short STAI) – 5 minutes

Anxiety assessment with parents/guardians and children at baseline, after completing the intervention, and before the mock MRI. The Short STAI is a 6-item, adapted version of the well-validated Spielberger State-Trait Anxiety Inventory Scale.³⁵ It distinguishes between general proneness to anxious behavior rooted in the personality and anxiety connected to a current state, and has been validated for use in children.³⁵

Demographics and Relevant History

Demographic and possible confounding information (age, sex, prior experience with medical imaging, experience with virtual reality, type of mobile phone) will be obtained through a data collection form. Data will be de-identified using a participant identification number.

Length of Stay (LoS)

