Outcomes will be reported at both the hospital and patient/family perspective, based on the data gathered in Phase 2 (**Table 4**); this includes the predictive non-sedation rates, length of hospital stay, and reductions in anxiety from the patient and family perspectives.

Stage 3: Multi-Level Cost-Effectiveness Modelling

Cost-Effectiveness will be modelled across the various scenarios identified and from multiple perspectives (i.e. hospital, patient/family). To support decision-making, we will determine the **incremental cost-effectiveness ratio (ICER)** of the intervention versus the control. ICER is a statistic used to summarise the cost-effectiveness, and is defined by the difference in cost between two possible interventions, divided by the difference in their effect; this represents the average incremental cost associated with 1 additional unit of the measure of effect. For our study, we will measure ICERS for multiple outcome variables that are measured in Phase 2.

Uncertainty Analysis

We expect the number of users, the average amount of consumables and equipment used, and the amount spent on promotional costs to fluctuate. Therefore, we will conduct a probabilistic uncertainty analysis around these program variables to determine sensitivity and what the expected range of cost-effectiveness might be. These values and distribution for the uncertainty analysis will be selected based on one-year data.

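### The primary pass/fail measures head stillness in one mock scan without IV or contrast, but it enters Phase 3 as a predicted non-sedation rate with no uncertainty on that step

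*Combined protocol and SAP*

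**What the plan says.** Section 4.4 defines the endpoint: "The primary outcome variable is likelihood of success (pass/fail) of the MRI simulation". Step 11 of the Implementation Plan describes MoTrak as "an objective head motion tracking system". Under Primary Measures, the sensor on the child's head serves "to determine the position of the head in space relative to a transmitter located within the simulator", and the one scoring rule given is: "The fail threshold is set at 3mm of movement in any of the positional displacements (x,y,z". The plan says this limit follows the hospital's imaging protocols.

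Step 11 adds that every child has the same kind of simulated scan, with 8 minutes in the bore, and: "We will not be simulating any invasive procedures that can sometimes occur during the MRI".

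The result is presented under the heading Predictive Success in Avoiding Sedation. The outputs table (the second Table 4) links it to better non-sedation rates for MRI scans. Section 4.5, Stage 2, lists the outcomes to be reported from Phase 2: "this includes the predictive non-sedation rates, length of hospital stay". None of these places limits the result to head examinations or to examinations without contrast.

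Section 4.3 takes a wider view of what an MRI asks of a child. Table 3 there lists as a target: "Improve skills required for successful MRI (e.g. holding breath". The possible VR content includes "Receiving numbing cream, and an IV", contrast where applicable, and knee, hand, foot, leg, body and shoulder coils as well as the head coil.

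**The concern.** The scored event is narrower than its label. A child can keep the head within 3 mm for 8 minutes and still need sedation for a real examination, because of refusal at the IV, a failed breath-hold, or movement of a limb being imaged. Conversely, a child can fail on head movement that would not matter when another body part is imaged.

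This matters mainly in Phase 3. Section 4.5 asks what is saved by converting a sedated case to a non-sedated one, and computes incremental cost-effectiveness ratios on outcomes measured in Phase 2. If a pass is read as a non-sedated MRI, the step from one to the other is treated as certain. The uncertainty analysis varies user numbers, consumables and equipment, and promotional spending. It does not vary this step.

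**Working it through.** **1. What the plan asks of the child, against what is scored.**

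| Requirement | Where the plan raises it | Scored in pass/fail? |
|---|---|---|
| Head still | 4.4, Primary Measures | Yes, 3 mm in x, y or z |
| Rest of body still | 4.3, list of possible coils | Only if the head moves 3 mm |
| Breath-holding | 4.3, Table 3 | No such task described |
| IV and contrast | 4.3, possible VR content | Not simulated |

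**2. The plan's only figures linking a simulator result to actual sedation** (Table 2, section 3.0).

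- Conversion overall: 283/(283 + 61) = 283/344 = 82.3%. This reproduces the stated 82%.
- Passers: 283 + 8 = 291. Still sedated: 8/291 = 2.7%, exact (Clopper-Pearson) 95% CI 1.2% to 5.3%. So P(non-sedated | pass) = 283/291 = 97.3%.
- Failures: 0 of 53 non-sedated. With zero events the exact 97.5% upper limit is 1 − 0.025^(1/53) = 6.7%.

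These children were referred patients prepared by a Child Life Specialist, and the documents do not say that passing meant the MoTrak 3 mm rule. The zero among failures is also partly a matter of policy: section 3.0 says that children under 7 must pass the simulator to have a non-sedated MRI. It therefore cannot show how many failures would have managed a real scan.

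**3. How the missing step enters a model.** Let p be an arm's pass rate, s = P(non-sedated | pass) and f = P(non-sedated | fail). Then

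non-sedation rate = p·s + (1 − p)·f.

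If s and f are the same in both arms, the between-arm difference is (p₁ − p₂)(s − f). Reading the pass rate as the non-sedation rate sets s = 1 and f = 0.

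Illustration with assumed pass rates of 80% and 60%, f = 0, and u = 1 − s: the difference is 20 × (1 − u) points.

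- u = 0: 20.0
- u = 2.7% (Table 2): 19.5
- u = 10%: 18.0
- u = 20%: 16.0
- u = 30%: 14.0

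If u differs by arm, the error can go either way. With an assumed 80% pass rate in both arms, and u of 2.75% in one and 20% in the other, non-sedation differs by 0.80 × 0.9725 − 0.80 × 0.80 = 0.778 − 0.640 = 13.8 points, although the pass rates are equal. Swapping the arms reverses the sign. The documents give no value of u for this trial.

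**4. Carry-over to other examinations, as illustration only.** The documents give no case mix. Suppose a share h of eligible cases is non-contrast head examinations, and the effect elsewhere is k times the effect there. Applying one pass-rate difference to all cases would then multiply the credited conversions by 1/(h + k(1 − h)):

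| k | h = 0.3 | h = 0.5 | h = 0.7 |
|---|---|---|---|
| 0 | 3.33 | 2.00 | 1.43 |
| 0.5 | 1.54 | 1.33 | 1.18 |
| 1 | 1.00 | 1.00 | 1.00 |
| 1.5 | 0.74 | 0.80 | 0.87 |

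Both h and k are assumptions. Depending on k, the factor is above, equal to or below 1, so the table shows that direction as well as size is open.

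**The case against.** The plan discloses part of this. Section 3.0 limits Phase 2 to a simulated MRI experience, step 11 says that the test is not a real MRI and has no invasive procedures, and section 4.5 calls the cost-effectiveness ratio a potential one with known limitations. The work is prototype evaluation. The coils, IV and contrast are only possible VR content, and breath-holding is a single example in a design table. Child anxiety is also listed among the primary measures, so distress is not judged by head motion alone. In Table 2, few simulator passers went on to sedation.

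Most of this stands, and it limits the point. But saying that a scan is simulated is not the same as limiting the inference to head stillness without an IV, and no such limit reaches the endpoint label, the outputs table or Stage 2. Anxiety scores do not enter the stated fail rule. Table 2 suggests a small gap in similar patients but does not validate this endpoint, and section 4.4 allows participants who are not scheduled for an MRI.

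A reader might infer three stronger things that the documents do not support:

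- That the cost model credits the pass-rate difference to every MRI at the hospital. The plan nowhere multiplies it by total volume; it speaks of modelling across scenarios.
- That the instrument is blind to body motion. Gross movement that shifts the head by 3 mm would register.
- That the comparison between preparation methods is undermined. All arms have the same assessment, so it stands as a comparison of head stillness.

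**Conclusion.** The point holds as one of labelling and of an unmodelled step. The primary outcome supports a conclusion about head stillness (3 mm) in a mock scan without IV or contrast. Calling it predicted sedation avoidance, and using it in Phase 3 as the predictive non-sedation rate without uncertainty, goes further than the measurement does.

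Neither the size nor the direction of any resulting error can be derived from the documents. The nearest evidence is the 2.7% of simulator passers still sedated, in a different population and under an unstated pass rule. It may be tempting to read the upper rows of the carry-over table as an estimated overstatement of up to 3.3-fold. That is not supported: it needs an unsourced case mix and no effect at all on every limb, body and contrast examination. This rests on the 3 mm head rule being the whole of the pass/fail definition; no other component is stated.

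**What to change.** In section 4.4, Primary Measures, define the primary outcome as head stillness (3 mm) in a simulated MRI without IV or contrast. Use the same wording in the outputs table and limit the Phase 2 conclusion to it.

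In section 4.5:

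- **Stages 2 and 3:** make P(non-sedated MRI | pass) and P(non-sedated MRI | fail) explicit model inputs. Use Table 2 as one source, and state its population and its unstated pass rule.
- **Uncertainty Analysis:** vary both probabilities alongside the variables already listed, and allow them to differ by arm in a sensitivity run.
- **Scenarios:** report results with the pass-rate difference carrying over to non-head or contrast examinations with no, half, the same and a larger effect. Split by administrative volumes where these are available; the documents do not say that volumes by body part or contrast can be obtained.

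A base case restricted to non-contrast head examinations should not be imposed. It would assume zero effect elsewhere, which is as untested as full effect.

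No new procedure or participant burden is needed. The cost is a little more modelling work and a wider cost-effectiveness range.
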